4.2.2 Timing of Dose Administration

Trial treatment should be administered on Day 1 of each cycle after all procedures/assessments have been completed as detailed on the Trial Flow Chart (Section 5.0). Trial treatment may be administered within a window of +/-3 days from the scheduled Day 1 of each cycle.

All trial treatments will be administered on an outpatient basis.

Pembrolizumab 200 mg will be administered as a 30-minute IV infusion every 3 weeks. Sites should make every effort to target infusion timing to be as close to 30 minutes as possible. However, given the variability of infusion pumps from site to site, a window of -5 minutes and +10 minutes is permitted (i.e., infusion time is 30 minutes: -5 min/+10 min). Vital signs should be monitored within 60 minutes prior to infusion and if reaction occurs every 15-30 minutes until symptoms resolve.

The Pharmacy Manual contains specific instructions for the preparation of the Pembrolizumab infusion fluid and administration of infusion solution.

4.2.3 Trial Blinding/Masking

This is an open-label trial; therefore, the investigators, research staff, and subject will know the treatment administered.

4.3 Randomization or Treatment Allocation

This is an open-label, single arm, phase II trial in which all enrolled subjects will receive the study drug.

4.4 Stratification

As a single arm study, there is no need for stratification of patients between arms.

4.5 Concomitant Medications/Vaccinations (allowed & prohibited)

Medications or vaccinations specifically prohibited in the exclusion criteria are not allowed during the ongoing trial. If there is a clinical indication for one of these or other medications or vaccinations specifically prohibited during the trial, discontinuation from trial therapy or vaccination may be required. Treating sub-investigators should discuss any questions regarding this with the Principal Investigator. The final decision on any supportive therapy or vaccination rests with the investigator and/or the subject's primary physician.

4.5.1 Acceptable Concomitant Medications

All treatments that the investigator considers necessary for a subject's welfare may be administered at the discretion of the investigator in keeping with the community standards of medical care. All concomitant medication will be recorded on the case report form (CRF) including all prescription, over-the-counter (OTC), herbal supplements, and IV medications and fluids. If changes occur during the trial period, documentation of drug dosage, frequency, route, and date may also be included on the CRF.

All concomitant medications received within 28 days before the first dose of trial treatment and 30 days after the last dose of trial treatment should be recorded. Concomitant medications administered up to 30 days after the last dose of trial treatment should be recorded for SAEs and ECIs as defined in Section 6.2.3.

4.5.2 Prohibited Concomitant Medications

Subjects are prohibited from receiving the following therapies during the Screening and Treatment Phase (including retreatment for post-complete response relapse) of this trial:

- Anti-cancer systemic chemotherapy or biological therapy
- Immunotherapy not specified in this protocol
- Chemotherapy not specified in this protocol
- Investigational agents other than pembrolizumab
- Live vaccines within 30 days prior to the first dose of trial treatment and while participating in the trial. Examples of live vaccines include, but are not limited to, the following: measles, mumps, rubella, chicken pox, yellow fever, rabies, BCG, and typhoid (oral) vaccine. Seasonal influenza vaccines for injection are generally killed virus vaccines and are allowed; however intranasal influenza vaccines (e.g. Flu-Mist®) are live attenuated vaccines, and are not allowed.
- Systemic glucocorticoids for any purpose other than to modulate symptoms from an event of clinical interest of suspected immunologic etiology. The use of physiologic doses of corticosteroids may be approved after consultation with the Sponsor.

Subjects who, in the assessment by the investigator, require the use of any of the aforementioned treatments for clinical management should be removed from the trial. Subjects may receive other medications that the investigator deems to be medically necessary.

The Exclusion Criteria describes other medications which are prohibited in this trial.

There are no prohibited therapies during the Post-Treatment Follow-up Phase.

4.6 Rescue Medications & Supportive Care

4.6.1 Supportive Care Guidelines

Subjects should receive appropriate supportive care measures as deemed necessary by the treating investigator. Suggested supportive care measures for the management of adverse events with potential immunologic etiology are outlined below and in greater detail in the ECI guidance document. Where appropriate, these guidelines include the use of oral or intravenous treatment with corticosteroids as well as additional anti-inflammatory agents if symptoms do not improve with administration of corticosteroids. Note that several courses of steroid tapering may be necessary as symptoms may worsen when the steroid dose is decreased. For each disorder, attempts should be made to rule out other causes such as metastatic disease or bacterial or viral infection, which might require additional supportive care. The treatment guidelines are intended to be applied when the investigator determines the events to be related to Pembrolizumab.

Note: if after the evaluation the event is determined not to be related, the investigator is instructed to follow the ECI reporting guidance but does not need to follow the treatment guidance (as outlined in the ECI guidance document). Refer to Section 4.2.1 for dose modification.

It may be necessary to perform conditional procedures such as bronchoscopy, endoscopy, or skin photography as part of evaluation of the event. Suggested conditional procedures, as appropriate, can be found in the ECI guidance document.

- **Pneumonitis:**

- For **Grade 2 events**, treat with systemic corticosteroids. When symptoms improve to Grade 1 or less, steroid taper should be started and continued over no less than 4 weeks.
- For **Grade 3-4 events**, immediately treat with intravenous steroids. Administer additional anti-inflammatory measures, as needed.
- Add prophylactic antibiotics for opportunistic infections in the case of prolonged steroid administration.

- **Diarrhea/Colitis:**

Subjects should be carefully monitored for signs and symptoms of enterocolitis (such as diarrhea, abdominal pain, blood or mucus in stool, with or without fever) and of bowel perforation (such as peritoneal signs and ileus).

- All subjects who experience diarrhea/colitis should be advised to drink liberal quantities of clear fluids. If sufficient oral fluid intake is not feasible, fluid and electrolytes should be substituted via IV infusion. For Grade 2 or higher diarrhea, consider GI consultation and endoscopy to confirm or rule out colitis.
- For **Grade 2 diarrhea/colitis** that persists greater than 3 days, administer oral corticosteroids.

- For **Grade 3 or 4 diarrhea/colitis** that persists > 1 week, treat with intravenous steroids followed by high dose oral steroids.
 - When symptoms improve to Grade 1 or less, steroid taper should be started and continued over no less than 4 weeks.
- **Type 1 diabetes mellitus (if new onset, including diabetic ketoacidosis [DKA]) or ≥ Grade 3 Hyperglycemia, if associated with ketosis (ketonuria) or metabolic acidosis (DKA)**
 - For **T1DM** or **Grade 3-4 Hyperglycemia**
 - Insulin replacement therapy is recommended for Type I diabetes mellitus and for Grade 3-4 hyperglycemia associated with metabolic acidosis or ketonuria.
 - Evaluate patients with serum glucose and a metabolic panel, urine ketones, glycosylated hemoglobin, and C-peptide.
- **Hypophysitis:**
 - For **Grade 2** events, treat with corticosteroids. When symptoms improve to Grade 1 or less, steroid taper should be started and continued over no less than 4 weeks. Replacement of appropriate hormones may be required as the steroid dose is tapered.
 - For **Grade 3-4** events, treat with an initial dose of IV corticosteroids followed by oral corticosteroids. When symptoms improve to Grade 1 or less, steroid taper should be started and continued over no less than 4 weeks. Replacement of appropriate hormones may be required as the steroid dose is tapered.
- **Hyperthyroidism or Hypothyroidism:**

Thyroid disorders can occur at any time during treatment. Monitor patients for changes in thyroid function (at the start of treatment, periodically during treatment, and as indicated based on clinical evaluation) and for clinical signs and symptoms of thyroid disorders.

 - **Grade 2** hyperthyroidism events (and **Grade 3-4** hypothyroidism):
 - In hyperthyroidism, non-selective beta-blockers (e.g. propranolol) are suggested as initial therapy.
 - In hypothyroidism, thyroid hormone replacement therapy, with levothyroxine or liothyronine, is indicated per standard of care.
 - **Grade 3-4** hyperthyroidism
 - Treat with an initial dose of IV corticosteroid followed by oral corticosteroids. When symptoms improve to Grade 1 or less, steroid taper should be started and continued over no less than 4 weeks. Replacement of appropriate hormones may be required as the steroid dose is tapered.

- **Hepatic:**
 - For **Grade 2** events, monitor liver function tests more frequently until returned to baseline values (consider weekly).
 - Treat with IV or oral corticosteroids
 - For **Grade 3-4** events, treat with intravenous corticosteroids for 24 to 48 hours.
 - When symptoms improve to Grade 1 or less, a steroid taper should be started and continued over no less than 4 weeks.

- **Renal Failure or Nephritis:**
 - For **Grade 2** events, treat with corticosteroids.
 - For **Grade 3-4** events, treat with systemic corticosteroids.
 - When symptoms improve to Grade 1 or less, steroid taper should be started and continued over no less than 4 weeks.

- **Management of Infusion Reactions:** Signs and symptoms usually develop during or shortly after drug infusion and generally resolve completely within 24 hours of completion of infusion.

Table 4 below shows treatment guidelines for subjects who experience an infusion reaction associated with administration of Pembrolizumab.

Table 4 Infusion Reaction Treatment Guidelines

| NCI CTCAE Grade | Treatment | Premedication at subsequent dosing |
|--|---|---|
| Grade 1 Mild reaction; infusion interruption not indicated; intervention not indicated | Increase monitoring of vital signs as medically indicated until the subject is deemed medically stable in the opinion of the investigator. | None |
| Grade 2 Requires infusion interruption but responds promptly to symptomatic treatment (e.g., antihistamines, NSAIDS, narcotics, IV fluids); prophylactic medications indicated for < =24 hrs | 
Stop Infusion and monitor symptoms. Additional appropriate medical therapy may include but is not limited to:
 
 IV fluids Antihistamines NSAIDS Acetaminophen Narcotics 
Increase monitoring of vital signs as medically indicated until the subject is deemed medically stable in the opinion of the investigator. If symptoms resolve within one hour of stopping drug infusion, the infusion may be restarted at 50% of the original infusion rate (e.g., from 100 mL/hr to 50 mL/hr). Otherwise dosing will be held until symptoms resolve and the subject should be premedicated for the next scheduled dose.
 
Subjects who develop Grade 2 toxicity despite adequate premedication should be
 | 
Subject may be premedicated 1.5h (± 30 minutes) prior to infusion of Pembrolizumab with:
 
Diphenhydramine 50 mg po (or equivalent dose of antihistamine).
 
Acetaminophen 500-1000 mg po (or equivalent dose of antipyretic).
 |

| NCI CTCAE Grade | Treatment | Premedication at subsequent dosing |
|---|--|------------------------------------|
| | permanently discontinued from further trial treatment administration. | |
| Grades 3 or 4 Grade 3: Prolonged (i.e., not rapidly responsive to symptomatic medication and/or brief interruption of infusion); recurrence of symptoms following initial improvement; hospitalization indicated for other clinical sequelae (e.g., renal impairment, pulmonary infiltrates) Grade 4: Life-threatening; pressor or ventilatory support indicated | Stop Infusion. Additional appropriate medical therapy may include but is not limited to: IV fluids Antihistamines NSAIDS Acetaminophen Narcotics Oxygen Pressors Corticosteroids Epinephrine Increase monitoring of vital signs as medically indicated until the subject is deemed medically stable in the opinion of the investigator. Hospitalization may be indicated. Subject is permanently discontinued from further trial treatment administration. | No subsequent dosing |
| Appropriate resuscitation equipment should be available in the room and a physician readily available during the period of drug administration. | | |

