4.2.1.2 Dose Modification

Adverse events (both non-serious and serious) associated with Pembrolizumab exposure may represent an immunologic etiology. These adverse events may occur shortly after the first dose or several months after the last dose of treatment. Adverse experiences will be graded and recorded throughout the study and during the follow-up period according to NCI CTCAE Version 4.0. Pembrolizumab must be withheld for drug-related toxicities and severe or life-threatening drug-related AEs as per Table 3 below. See Section 4.6.1 and Events of Clinical Interest Guidance Document for supportive care guidelines, including use of corticosteroids.

**Table 3
Dose Modification Guidelines for Drug-Related Adverse Events**

| Toxicity | Hold Treatment For Grade | Timing for Restarting Treatment | Discontinue Subject |
|----------------------------------|--------------------------|---------------------------------|--|
| Diarrhea/Colitis | 2-3 | Toxicity resolves to Grade 0-1. | Toxicity does not resolve within 12 weeks of last dose or inability to reduce corticosteroid to 10 mg or less of prednisone or equivalent per day within 12 weeks. |
| | 4 | Permanently discontinue | Permanently discontinue |
| AST, ALT, or Increased Bilirubin | 2 | Toxicity resolves to Grade 0-1 | Toxicity does not resolve within 12 weeks of last dose. |

| Toxicity | Hold Treatment For Grade | Timing for Restarting Treatment | Discontinue Subject |
|---|--------------------------|---|--|
| | 3-4 | Permanently discontinue | Permanently discontinue |
| Type 1 diabetes mellitus (if new onset) or Hyperglycemia | T1DM or 3-4 | Hold Pembrolizumab for new onset Type 1 diabetes mellitus or Grade 3-4 hyperglycemia associated with evidence of beta cell failure. | Resume Pembrolizumab when patients are clinically and metabolically stable. |
| Hypophysitis | 2-3 | Toxicity resolves to Grade 0-1 | Toxicity does not resolve within 12 weeks of last dose or inability to reduce corticosteroid to 10 mg or less of prednisone or equivalent per day within 12 weeks. |
| | 4 | Permanently discontinue | Permanently discontinue |
| Hyperthyroidism | 3 | Toxicity resolves to Grade 0-1 | Toxicity does not resolve within 12 weeks of last dose or inability to reduce corticosteroid to 10 mg or less of prednisone or equivalent per day within 12 weeks. |
| | 4 | Permanently discontinue | Permanently discontinue |

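### Section 4.6.1 suggests a later steroid start for Grade 3-4 diarrhea/colitis (more than 1 week) than for Grade 2 (more than 3 days), so the written default runs against severity

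*Combined protocol and SAP*

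**What the plan says.** The diarrhea/colitis entry of Section 4.6.1 (Supportive Care Guidelines) sets two steroid triggers, both based on how long the event lasts:

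- Grade 2: an event "that persists greater than 3 days, administer oral corticosteroids".
- Grade 3 or 4: an event "that persists > 1 week, treat with intravenous steroids followed by high dose oral steroids".

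Section 4.2.1.2 (Dose Modification) directs investigators to this text and to one other source: "See Section 4.6.1 and Events of Clinical Interest Guidance Document for supportive care guidelines, including use of corticosteroids". The other source is not among the documents supplied.

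The opening of Section 4.6.1 describes the measures as suggested and leaves supportive care to the treating investigator's judgement. It asks for attempts to rule out other causes, including infection, and says the treatment guidance applies once the event is judged related to pembrolizumab. Table 3 covers holding and stopping pembrolizumab for diarrhea/colitis (hold at Grade 2-3, permanent discontinuation at Grade 4). It does not say when steroids should start.

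**The concern.** Within one entry, the sicker patient gets the more intensive regimen but a later start. A persistence criterion appears at both levels, so the existence of a wait is not the complaint. The complaint is that the wait lengthens as the grade rises.

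This does not fit the rest of the protocol. Table 10 (Section 6.2.4) describes Grade 4 as life-threatening and calling for urgent intervention. The diarrhea/colitis entry itself tells investigators to watch for signs of bowel perforation. An investigator who applied the bullet literally could start steroids later in severe or life-threatening drug-related colitis than in moderate colitis. What is at stake is the safety of the occasional patient, all of whom are 60 or older, and not the inference from the trial.

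**Working it through.** **1. The two triggers.** Grade 2: more than 3 days. Grade 3-4: more than 1 week, that is, 7 days. Difference: 7 − 3 = 4 days. Ratio: 7 / 3 ≈ 2.3.

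**2. The other steroid entries in Section 4.6.1.**

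| Disorder | Grade 2 | Grade 3-4 | Wait before steroids |
|---|---|---|---|
| Pneumonitis | "treat with systemic corticosteroids. When symptoms improve to Grade 1 or less", taper | "immediately treat with intravenous steroids" | none at either level |
| Hypophysitis | "treat with corticosteroids. When symptoms improve to Grade 1 or less", taper | "treat with an initial dose of IV corticosteroids followed by oral corticosteroids" | none at either level |
| Hepatic | IV or oral steroids | IV steroids for 24 to 48 hours | none at either level |
| Renal failure/nephritis | steroids | systemic steroids | none at either level |
| Diarrhea/colitis | oral steroids | IV, then high-dose oral | 3 days, then 7 days |
| Hyperthyroidism | no steroid instruction | "Treat with an initial dose of IV corticosteroid followed by oral corticosteroids" | none |

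Five disorders carry a steroid instruction at both levels. Four have no wait at either. One, diarrhea/colitis, has a wait at both, and it is longer at the higher grades.

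**3. Search for an earlier trigger elsewhere.** Table 3 deals with the study drug. Section 4.5.1 allows any treatment the investigator considers necessary. Section 4.5.2 exempts steroids for suspected immune events from the prohibition. None of these states when steroids should start in Grade 3-4 colitis.

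**4. How many patients could be affected.** The plan gives no figure, so this uses the Phase I data in Section 3.1.2.

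Inputs: Grade 3-5 drug-related diarrhea 0.7% in melanoma patients; no such event among 38 lung cancer (NSCLC) patients, whose only Grade 3-5 event was a pulmonary edema; planned sample 40. Carrying these rates over to AML is an assumption.

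- Central: 0.007 × 40 = 0.28 patients. Chance of at least one = 1 − 0.993^40 = 0.245, or 24%.
- Lower end: 0/38 × 40 = 0 patients.
- Upper end: this needs the melanoma denominator, which the protocol does not state. Subtracting the 38 NSCLC patients from the 479 with safety data gives 441, but that cannot be the denominator: 7/441 = 1.6% and 8/441 = 1.8%, so 1.7% is impossible; 8/441 = 1.8% and 9/441 = 2.0%, so 1.9% is impossible; 9/441 = 2.0% and 10/441 = 2.3%, so 2.2% is impossible. The section reports all three for melanoma.
- If the melanoma percentages given to one decimal (0.7, 1.7, 1.9, 2.2, 2.7, 2.9, 3.2) share one denominator of at most 479, only 411 or 412 reproduces them all. With 411 the counts are 3, 7, 8, 9, 11, 12 and 13.
- Exact (Clopper-Pearson) 95% upper limit for 3/411 = 2.12%, giving 0.0212 × 40 = 0.85 patients and 1 − (1 − 0.0212)^40 ≈ 0.575. For 3/412 the limit is 2.11%, giving 0.845 patients and about 0.574.

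The range is therefore 0 to about 0.85 of 40 patients, with a chance of at least one of up to 57-58%. These are counts of severe diarrhea. Patients whose steroids were actually delayed would be fewer.

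**5. Effect on the statistical design.** None. Section 7.3 counts a drug-related toxicity once it leads to holding or stopping pembrolizumab, and Table 3 triggers that by grade, whenever steroids begin. The efficacy endpoint, its test and the power statement do not involve this bullet.

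**The case against.** The strongest case on the other side has four parts.

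*The text is guidance.* It says when to give steroids, not that they must be withheld before then. Sections 4.5.1, 4.5.2 and 4.6.1 together leave the investigator free to treat earlier. This stands. A reader might infer that the protocol forbids or blocks early steroids in severe colitis; it does not. Discretion still does not make the written default right.

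*Other protections carry no wait.* Fluids, consideration of GI consultation and endoscopy, and the Table 3 drug hold or stop all apply at once. A patient who worsens after more than 3 days at Grade 2 has already met the oral steroid trigger. This limits the harm, but none of these measures sets the steroid start for an event that presents at Grade 3 or 4.

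*The ECI guidance document may say something different.* Section 4.2.1.2 names it alongside Section 4.6.1, and Section 4.6.1 says it has more detail. This stands as a limit. A reader might infer that investigators are in fact told to wait a week; the documents show what the bullet says, not the whole instruction received. If the guidance sets an earlier trigger, the two sources conflict and the bullet still needs correcting.

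*Only the direction is shown to be wrong.* A reader might infer that the protocol proves immediate IV steroids to be the right rule for Grade 3 colitis. It does not: the entries without a wait use no persistence criterion at all, so they cannot fix the right interval for colitis. The inversion directly supports only a Grade 3-4 trigger no later than Grade 2. Removing the wait is a preference, supported by analogy with the other entries and by the Grade 4 definition.

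Time for an infection work-up is not a sufficient defence. That need exists at Grade 2 as well, where the wait is shorter.

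**Conclusion.** The concern holds in a limited form. As written, the bullet sets the Grade 3-4 steroid trigger 4 days later than the Grade 2 trigger, this is the only entry in Section 4.6.1 where the wait grows with grade, and no other supplied text overrides it. It should be fixed as a low-frequency patient-safety correction.

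Confidence is high on the bullet's wording and lower on what investigators are told overall, because the ECI guidance was not seen. The expected number of severe cases is well below one in 40. That estimate assumes that solid-tumor rates carry over to AML, and its upper end also assumes that the quoted melanoma percentages share one denominator. It would be wrong to read the point as a threat to the trial's conclusions.

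**What to change.** At minimum, reword the Grade 3-4 diarrhea/colitis bullet in Section 4.6.1 so that its steroid trigger is no later than the Grade 2 trigger, at most 3 days. Preferably, delete the one-week persistence clause, so that IV steroids followed by high-dose oral steroids apply once a Grade 3 or 4 event is judged related to pembrolizumab. The attempt to rule out infection that the section already requests would stay in place. Check the new wording against the ECI guidance document first, so that the two sources agree.

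The cost is a minor amendment with IRB submission and a notice to the treating sub-investigators at the single center. No procedures, patients or analyses are added.
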